## Participants.

Participants will be 60 7- to 11-year-olds with ASD: 30 will be randomly assigned to training and 30 to waitlist. It is anticipated that 80 children with ASD will be recruited to obtain a final sample with artifact free data.

## Recruitment & Diagnostic Procedures.

Children will be recruited from the institution's research participant registry, clinical referrals, and advertising. Recruitment will also target the local ASD community (service providers, clinicians, and parent advocacy groups). Participants will also be recruited via fliers, bulletins and local media.

*Intelligence* will be assessed using the Wechsler Abbreviated Scale of Intelligence-II (WASI-II) and the WASI-II verbal comprehension index will be used to control for individual and group differences in language ability. *Diagnosis* of autism spectrum disorder will be made using DSM-V criteria following administration of gold-standard measures for assessment of ASD symptoms: the Autism Diagnostic Interview (ADI-R) and the Autism Diagnostic Observation Schedule-2 (ADOS-2). The presence and potential impact of ADHD symptoms will be assessed via the Child Behavior Checklist (CBCL).

*Exclusionary criteria* for all participants will be assessed by administration of a screening interview during enrollment and will include presence of seizures; medical disorders or injuries with implications for the central nervous system or that require regular psychoactive medication that alter EEG processes; and non-English speaking children. An additional exclusion criterion for children with ASD is IQ < 80.

Assessment Procedures. Electrophysiological and behavioral responses will be recorded. Behavioral and electrophysiological measures will be collected via computer to control social demands between tasks used to assess ERP response and behavior, which is important for studying executive control in ASD.

*Electrophysiological measures of executive control.* Two ERP assessments will be used to measure neural function. Practice will be given before both tasks to ensure understanding. The *Child ANT* consists of a cue followed by congruent or incongruent trial in equal proportion for 108 trials. Stimuli are cartoon fish with arrow shaped gills, mice with arrow shaped noses, and birds with arrow shaped beaks. Trials begin with a cue presented for 150 ms, followed by a fixation of 450 ms. The target and flankers follow and remain until a response is made (left/right button press) corresponding to the direction of the central target (e.g., a fish) or 2000 ms elapse. This method has been used with children without ASD as young as 4 years of age. The *Go/Nogo* task consists of a cue followed by a go or nogo stimulus. The cue is presented for 500 ms, followed by a go or nogo stimulus presented for 500 ms at 1500 ms after the cue. The next trial follows 500 ms after a button press or 1000 ms after no response (Nogo trials). 150 total trials will be presented with 3 breaks. The visual cued go/nogo method has been used with 6-year-olds.

*Electrophysiological acquisition.* Electrical brain activity will be examined using high-density EEG (128 channel Hydrocel Geodesic Sensor Net, GSN; EGI, Eugene OR) in an electrically shielded, sound-attenuated laboratory. The HCGSN is reliable and application is fast, making it an ideal device for EEG collection with children. Net preparation will follow manufacturer specifications. Stimuli will be presented via E-Prime-2 software (PST, Inc, Pittsburgh PA) while children sit 75 cm from the screen. A large screen will obscure the back of the monitor and the computer equipment from the child's view. Impedances will be kept below 50 k $\Omega$ . Amplification will be set at 1000; data will be filtered at 0.1 Hz and 200 Hz. Continuous EEG recording will occur at 500 Hz and signals will be referenced to the vertex electrode.

*Aim 2 behavioral assessment.* Data will be collected during three lab visits, beginning with diagnostic and cognitive assessment followed by ERP assessment (Child ANT, Go/Nogo). In addition, Theory of Mind will be assessed with five tasks: Social Attribution Task, Perception Knowledge, Location Change False Belief, Unexpected-contents False Belief, and the Theory of

Mind Test. These tasks allow for sufficient variability to detect individual differences at the planned age range. Parent and teacher report of social function and social symptoms will be collected via the Social Skills Improvement System and Social Responsiveness Scale-2, respectively.

*Aim 3 behavioral assessment.* Data will be collected before and after training with the same battery of tasks. In addition to ERP (Child ANT, Go/Nogo), the behavioral assessment battery will include executive control measures (Stroop, Change Task, and Hungry Donkey Task) and a brief (non-conflict) task (Backward Digit Span). Parent and teacher report of executive function will also be collected at baseline using the BRIEF questionnaire. At post-testing, ERP, behavioral measures of executive control and parent/teacher report of executive control will be collected again. TOM tasks (SAT, Perception Knowledge, False Belief tasks, and the TOM Test) as well as parent and teacher report measures (SSIS, SRS) will also be collected. Results from Aims 1-2 will be used to further inform decisions about which measures to prioritize in post-training testing, which will be important for obtaining artifact free ERP data from the majority of children with ASD across time points.

Summary of measures in Electrophysiological and Behavioral Battery with children with ASD

Construct and Type	Measure Name and Citation
Autism Symptoms-Diagnosis	Autism Diagnostic Observation Schedule-2 (ADOS-2)
Autism Symptoms-Diagnosis	Autism Diagnostic Interview-Revised (ADI-R)
Intelligence/Verbal Intelligence	Wechsler Abbreviated Scale of Intelligence-2 (WASI-2)
Conflict Processing-ERP	Cued Go/Nogo
Conflict Processing-ERP	Child Attention Network Task (Child ANT)
Conflict Processing	Hungry Donkey Task
Conflict Processing	Change Task
Conflict Processing	Stroop Task
Exec. Control at home/school	BRIEF Parent and Teacher Surveys
Theory of Mind	Social Attribution Task (SAT)
Theory of Mind	Perception Knowledge
Theory of Mind	Location Change False Belief
Theory of Mind	Unexpected-contents False Belief
Theory of Mind	TOM Test
Social function at home/school	Social Skills Improvement System-Parent & Teacher Surveys (SSIS)
Social symptoms home/school	Social Responsiveness Scale-Parent & Teacher Surveys (SRS)
*Working Memory	Backward Digit Span

Note: Measures with \* will serve as contrasts to Executive Control Measures for Brain-Behavior comparisons. *Italicized measures are parent report.*

**Intervention: Brief computerized executive control training.** Children with ASD will be randomly assigned to either computer training or a waitlist control condition following a list generated by a staff member independent of the research team using a computer algorithm to generate a random order. Training designed to directly target executive control and attention will follow the basic protocol used with TD children. Ten training visits will occur over a 2-3-month period. A research assistant or graduate student will conduct visits, so the assessment team may remain naïve to treatment status. *Four training exercises* appropriate for typically developing children 6 years and older will be used, including anticipation, stimulus discrimination, conflict resolution, and inhibition tasks. *Criteria for progress* throughout each level are based on the number of consecutive correct responses. Our current pilot study is evaluating the optimal duration. In more recent work, Rueda and her colleagues have used a 10-hour training protocol instead of a 5-hour protocol. Based on our current piloting, we plan to deliver the same duration of training to each participant, such that if children with ASD pass all training activities a shorter duration, additional training will be provided in conflict resolution and inhibition tasks until the training hours are completed. Both groups will return to the lab for follow-up testing 2-3 months after baseline assessment, after which the waitlist group will be offered training if it is efficacious. *Training modifications* will be made following piloting if needed and may include: allowing

children to pick characters that are highly motivating, reducing language demands, and extending tasks for older children.

*Attrition* will be addressed by recruiting additional participants. Attrition is expected to be very low, given 0% attrition with similar, brief computer training for individuals with ASD.

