### Statistical Analyses.

To assess potential training effects on ERP components, repeated-measures ANCOVA will be calculated by comparing groups (trained/waitlist) and within subjects effects of condition (congruent/ incongruent or Go/Nogo) and time point (baseline/post treatment) and number of trials covaried. ANCOVA controlling for baseline performance will be used to test executive control behavior (Hungry Donkey, Stroop, Change Task) and parent/teacher BRIEF scores pre/post training. Second, to test generalization of training to social measures, ANCOVA controlling for baseline will be used to assess differences in social cognition (TOM composite), social function (SSIS), and social symptoms (SRS). As a control condition, ANCOVA will also be used to measure potential changes with a non-conflict task (Backward Digit Span). *Power:* Given the proposed sample size of 30 children per group and a correlation of 0.3 or greater, with power of 0.8 and alpha = 0.05, a moderate effect size ( $f^2 = 0.21$ ) would be detected via repeated measures ANCOVA. ANCOVA with 1 covariate will have 0.8 power to detect a large effect size ( $f^2 = 0.37$ ) for behavioral and parent report tasks after training.

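### The protocol says WASI-II verbal comprehension will be used to control for language ability, but no training model includes it; the models and that sentence need to be reconciled.

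*Combined protocol and SAP*

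**What the plan says.** In the combined protocol and SAP, under Recruitment & Diagnostic Procedures: "the WASI-II verbal comprehension index will be used to control for individual and group differences in language ability". The sentence names no aim or analysis to which it is limited.

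Under Statistical Analyses, the models for the training comparison are:

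- **ERP components:** repeated-measures ANCOVA with group, condition "and time point (baseline/post treatment) and number of trials covaried".
- **Executive tasks and BRIEF:** "ANCOVA controlling for baseline performance will be used to test executive control behavior", with BRIEF scores handled in the same way.
- **Social outcomes (theory-of-mind composite, SSIS, SRS):** ANCOVA controlling for baseline.
- **Backward Digit Span:** ANCOVA, no covariate named.

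The power statement for the behavioural and parent-report outcomes reads "ANCOVA with 1 covariate will have 0.8 power to detect a large effect size", with the effect given as f² = 0.37.

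Under Participants: "Participants will be 60 7- to 11-year-olds with ASD: 30 will be randomly assigned to training and 30 to waitlist". The Intervention paragraph describes a computer-generated random order and mentions no stratification. Age appears in no model, and no section says that it will be adjusted for.

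**The concern.** One section commits to using verbal comprehension as a control, while the only section that defines models leaves it out. An analyst who follows the model definitions ignores the commitment, and one who honours the commitment departs from the model definitions and from the covariate count behind the power figure.

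Two things are at stake. First, covariate choice is left open across many outcomes: two ERP tasks, three executive tasks, parent and teacher BRIEF, the theory-of-mind composite, SSIS, SRS and digit span. Whether to include verbal comprehension could then be decided after results are seen. Second, a value already collected may go unused. The plan itself describes the effect its behavioural ANCOVAs can detect as large, so any added precision would be useful if verbal comprehension predicts post-test scores beyond the baseline score.

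**Working it through.** **1. Inputs.** From the documents: N = 60 (30 per group), alpha 0.05, target power 0.80, one covariate, stated effect 0.37. Not in the documents: the partial correlation *pr* between the added covariate(s) and the post-test score, given baseline. I take 0 to 0.5 as an assumed range.

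**2. The plan's own figure.** For a two-group ANCOVA the test is F with 1 and 60 − 2 − c degrees of freedom (c = number of covariates) and noncentrality λ = f² × N. With c = 1, the degrees of freedom are 1 and 57.

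- 0.37 read as Cohen's f: λ = 0.37² × 60 = 8.21, power 0.804. The effect detectable with exactly 0.80 power is f = 0.368.
- 0.37 read literally as f²: λ = 0.37 × 60 = 22.2, power 0.996.

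The stated power of 0.80 is reproduced only if 0.37 is f. The f² label appears to be wrong, and everything below uses f = 0.368.

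**3. Adding verbal comprehension.** The added covariate reduces residual variance by the factor 1 − pr², so λ = 60 × 0.368² / (1 − pr²) = 8.125 / (1 − pr²). The degrees of freedom are 1 and 56, or 1 and 55 if age is also added (pr is then the joint value for both).

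| Assumed pr | λ | Power, one added covariate | Power, two added | Detectable f at 0.80 power | Equivalent N, 60/(1 − pr²) |
|---|---|---|---|---|---|
| 0 | 8.13 | 0.800 | 0.800 | 0.368 | 60 |
| 0.2 | 8.46 | 0.816 | 0.816 | 0.361 | 62.5 |
| 0.3 | 8.93 | 0.836 | 0.835 | 0.351 | 65.9 |
| 0.4 | 9.67 | 0.864 | 0.863 | 0.337 | 71.4 |
| 0.5 | 10.83 | 0.899 | 0.899 | 0.319 | 80 |

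At pr = 0 power goes from 0.8002 to 0.7999 with one added covariate and to 0.7997 with two, a loss of at most 0.05 percentage point.

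**4. Chance imbalance.** The standard error of a standardised baseline difference is √(2/30) = 0.26, so its 95% range is about ±0.51 SD. By the normal approximation, a difference of 0.3 SD or more has probability about 25% for any one covariate, and one of 0.5 SD or more about 5%.

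**5. ERP model.** The training effect there is the group-by-time term (with or without condition). A covariate that is constant over time and enters only as a main effect cancels from a before-after contrast, so it does not sharpen that term. It can help only through its interaction with time, or in a post-test model adjusted for the baseline ERP value. The table above does not apply to the ERP outcomes.

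**The case against.** The strongest reply is that the sentence was not written for the randomised comparison. The document comes from a wider programme: it refers to Aims 1-2, whose analyses are not included, and it lists exclusions for all participants before an extra one for children with ASD. Controlling for group differences in language suits a comparison of diagnostic groups better than a randomised contrast, where no systematic difference is expected. This is plausible, and it means a reader should not infer that a promised control has definitely been dropped. But the sentence carries no such limit, and in this document the only groups analysed are trained and waitlist. The inconsistency therefore stands, although limiting the sentence would also resolve it.

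Other stronger readings are tempting and are not supported:

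- *That precision is lost.* Most outcomes are already adjusted for the same measure taken 2-3 months earlier, which may absorb much of the language-related variance. The documents give no correlation. Partial correlations of 0.2 to 0.3 add only about 2 to 4 points of power, and nothing in the documents supports the 0.5 needed to reach 0.90.
- *That omitting age breaks a commitment.* No section promises age adjustment, and the plan does not say whether outcomes are raw or age-standardised scores.
- *That a serious imbalance is likely, or that the estimate is biased.* A large imbalance is possible but not probable, and randomisation protects the estimate on average.

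**Conclusion.** The point holds as a discrepancy between two sections with a nearly free remedy. Verbal comprehension is named as a control without restriction, appears in no training model, and is not counted in the power statement. For the ANCOVA outcomes the benefit of including it ranges from nil to about 10 points of power over assumed partial correlations of 0 to 0.5, at a cost below 0.1 point if it explains nothing. These figures rest on reading 0.37 as Cohen's f, on 60 analysed children, and on correlations that the documents do not supply. No gain has been calculated for the ERP outcomes. The matter is worth correcting before analysis, but it does not threaten the validity of the randomised comparison.

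**What to change.** In Statistical Analyses:

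1. Name baseline WASI-II verbal comprehension as a prespecified covariate, alongside the baseline value of the outcome, in each post-test ANCOVA: executive tasks, BRIEF, theory-of-mind composite, SSIS, SRS and Backward Digit Span. State the baseline covariate for Backward Digit Span explicitly.
2. For the ERP outcomes, either use a post-test ANCOVA adjusted for the baseline ERP value with verbal comprehension added, or include verbal comprehension with its interaction with time.
3. Change the covariate count in the power statement to match, and correct the label of 0.37 from f² to f.
4. If the sentence under Recruitment & Diagnostic Procedures was meant only for Aims 1-2, say so there, and state that the training models do not adjust for verbal comprehension.

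Recommended in addition: include baseline age in the same models, given the 7-11 year range and the absence of any described stratification.

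The cost is a few sentences and, in each post-test ANCOVA, one degree of freedom, or two with age. The WASI-II is already in the battery, so no new data are needed.

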### **Analyses.**

Electrophysiological Analyses. Trials will be processed using Netstation (EGI; Eugene, OR). Data will be filtered with a 0.1-30 Hz bandpass filter. Then data will be segmented into target-locked epochs around the stimulus. Segment files will be inspected for artifacts using both artifact detection tools and visual inspection of files with recoded IDs (to reduce potential for bias) by a staff member naïve to group assignment. To ensure that number of trials discarded due to artifact does not bias the results, the number of trials will be included in analyses as a covariate. Data will be averaged for stimulus type, and re-referenced to an average reference based on previous reports.

### Statistical Analyses.

To assess potential training effects on ERP components, repeated-measures ANCOVA will be calculated by comparing groups (trained/waitlist) and within subjects effects of condition (congruent/ incongruent or Go/Nogo) and time point (baseline/post treatment) and number of trials covaried. ANCOVA controlling for baseline performance will be used to test executive control behavior (Hungry Donkey, Stroop, Change Task) and parent/teacher BRIEF scores pre/post training. Second, to test generalization of training to social measures, ANCOVA controlling for baseline will be used to assess differences in social cognition (TOM composite), social function (SSIS), and social symptoms (SRS). As a control condition, ANCOVA will also be used to measure potential changes with a non-conflict task (Backward Digit Span). *Power:* Given the proposed sample size of 30 children per group and a correlation of 0.3 or greater, with power of 0.8 and alpha = 0.05, a moderate effect size ( $f^2 = 0.21$ ) would be detected via repeated measures ANCOVA. ANCOVA with 1 covariate will have 0.8 power to detect a large effect size ( $f^2 = 0.37$ ) for behavioral and parent report tasks after training.

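### ERP training effects are tested as change from baseline, not adjusted for baseline; if the pre-post correlation is 0.3 this inflates the variance 1.54-fold, and if it is 0.7, 1.18-fold

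*Combined protocol and SAP*

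**What the plan says.** The Statistical Analyses section uses two different models for training effects.

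- **ERP components:** "repeated-measures ANCOVA will be calculated by comparing groups (trained/waitlist) and within subjects effects of condition", followed by "time point (baseline/post treatment) and number of trials covaried". Baseline ERP is therefore one level of the outcome. Trial count is the only covariate, consistent with Electrophysiological Analyses ("the number of trials will be included in analyses as a covariate"). The section does not name the term that tests training.
- **Executive control tasks and BRIEF:** "ANCOVA controlling for baseline performance will be used to test executive control behavior".
- **TOM composite, SSIS and SRS:** "ANCOVA controlling for baseline will be used to assess differences in social cognition".

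No reason is given for treating ERP differently. The power statement begins "Given the proposed sample size of 30 children per group and a correlation of 0.3 or greater" and gives 0.21 for the repeated-measures model. It then says that "ANCOVA with 1 covariate will have 0.8 power to detect a large effect size", with the value 0.37. Both values are printed as f². The section does not say which measurements the correlation of 0.3 relates.

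Baseline ERP will be available. Under Aim 3 behavioral assessment, "Data will be collected before and after training with the same battery of tasks", and that battery includes both ERP tasks.

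**The concern.** With two time points, a group-by-time test is a comparison of mean change between groups. Group-by-time-by-condition is the same comparison applied to the condition difference (incongruent versus congruent, or Go versus Nogo). Subtracting the baseline fixes its coefficient at 1. ANCOVA estimates the coefficient, which with equal variances is r. When r is well below 1, subtraction carries baseline noise into the outcome.

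The ERP components are the trial's neural outcomes. There are only 30 children per group, and the Participants section expects to recruit 80 children to obtain 60 with usable recordings. A model that discards precision is costly here, and the baseline needed to recover it is already collected.

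**Working it through.** **Inputs.** From the plan: 30 per group, alpha 0.05, power 0.80, correlation of at least 0.3. Assumed here: equal variances at the two times, r = 0.5 and r = 0.7 as further values, and a true effect of 0.70 SD of the tested quantity, which is about what ANCOVA detects with 80% power at r = 0.3.

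**The plan's own figures.** These come from the noncentral F distribution.

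- *ANCOVA, one covariate:* λ = 60f² with 1 and 57 df. Power of 0.80 needs λ = 8.12, so f = √(8.12/60) = 0.368. The printed 0.37 reproduces if read as f.
- *Group-by-time, two time points:* λ = 60 × 2 × f²/(1−r) with 1 and 58 df. At r = 0.3, f = √(8.12 × 0.7/120) = 0.218. The printed 0.21 does not reproduce exactly, since power at f = 0.21 is 0.77. It fits at r of about 0.35.
- *Read literally as f²,* both values give power above 0.99.

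The comparison below does not depend on these figures.

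**Variance per child, in units of σ².**

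- Change score: 2(1−r)
- ANCOVA: 1−r²
- Ratio: 2(1−r)/[(1−r)(1+r)] = 2/(1+r)

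**Power at d = 0.70.** λ = 30d²/(2v) = 7.35/v, where v is the variance above, with 58 df for change and 57 for ANCOVA. The detectable effect is the d that gives 80% power.

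| r | v, change | v, ANCOVA | Ratio | λ, change / ANCOVA | Power, change / ANCOVA | Detectable SD, change / ANCOVA |
|---|---|---|---|---|---|---|
| 0.3 | 1.40 | 0.91 | 1.54 | 5.25 / 8.08 | 0.615 / 0.798 | 0.87 / 0.70 |
| 0.5 | 1.00 | 0.75 | 1.33 | 7.35 / 9.80 | 0.760 / 0.868 | 0.74 / 0.64 |
| 0.7 | 0.60 | 0.51 | 1.18 | 12.25 / 14.41 | 0.931 / 0.962 | 0.57 / 0.53 |

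At r = 0.3 the change-score test would need about 30 × 1.54 = 46 children per group to match ANCOVA with 30.

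**Finite-sample check.** Estimating the baseline slope multiplies the ANCOVA variance by about 1 + 1/(60−4) = 1.018. The ratios become 1.51, 1.31 and 1.16. A simulation with an unrelated trial-count covariate in both models gave ratios of 1.50, 1.32 and 1.14, and power of 0.61 against 0.78, 0.74 against 0.85, and 0.93 against 0.96. Both estimates averaged 0.70, so neither is biased.

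**If 0.3 holds among all four condition-by-time measures.**

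- *Condition average:* variance (1+0.3)/2 = 0.65 and pre-post covariance 0.30, so r = 0.30/0.65 = 0.46 and the ratio is 2/1.46 = 1.37.
- *Condition difference:* pre-post covariance 0.3 − 0.3 − 0.3 + 0.3 = 0, so r = 0 and the ratio is 2.0. Power at 0.70 SD is 0.47 for change and 0.76 for ANCOVA.

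**If the group main effect were the test.** Averaging over both times halves the effect, and the variance of the average is (1+r)/2. On the scale above this is 4 × (1+r)/2 = 2(1+r), or 2.6 at r = 0.3, which is worse than 1.4 for the change score.

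**The case against.** The strongest reply is that the plan contains no error. A group-by-time analysis of a randomised trial is valid, and the ERP power statement refers to the model that is planned. The ERP outcome also has a within-child condition factor that the other outcomes lack, so a different model is not in itself a contradiction. All of this is correct, and the point is one of efficiency only.

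It can also be said that materiality is not established. The test term is inferred, 0.3 is a floor and may not be a pre-post correlation, and at r = 0.7 the gain is only 0.93 to 0.96 in power. This stands as a limit on size. It does not rescue the planned model: both candidate interaction terms are change-score contrasts, and with equal variances and r below 1 ANCOVA is never less precise apart from the small cost of estimating the slope.

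Two technical objections have some force. First, the simulation took trial count as unrelated to amplitude; precision with a related covariate was not examined. Second, one common baseline slope cannot be optimal for both the condition average (0.46 in the four-measure example) and the condition difference (0). In that example a common slope gave simulated ratios of about 1.29 and 1.84, against 1.33 and 2.00 with separate slopes. Most of the gain survives, but separate slopes are better.

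**Conclusion.** The concern holds as a loss of precision, not as bias. The planned ERP analysis has 2/(1+r) times the variance of a baseline-adjusted one: 1.54 at r = 0.3, 1.33 at r = 0.5 and 1.18 at r = 0.7, or about 1.51, 1.31 and 1.16 once slope estimation is allowed for. The loss is substantial near the plan's floor and small at 0.7 or above. If 0.3 applies among all four measures, the condition difference fares worst.

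These sizes assume equal variances at the two times and treat r as the pre-post correlation of the quantity actually tested, which the plan does not give. The change should be made because it costs almost nothing and matches the method already chosen for the other outcomes.

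**What to change.** 1. For each ERP task, model post-training amplitude with the corresponding baseline amplitude as a covariate. Two ANCOVAs would do: the condition average on its baseline average, and the condition difference on its baseline difference. An equivalent mixed model by condition should allow separate baseline slopes for the average and the difference.
2. Keep number of trials as a covariate.
3. Name group and group-by-condition at post-test as the tests of training.
4. Restate the ERP detectable effect for this model in SD units, over a stated range of r such as 0.3 to 0.7, and say which correlation r is. The present 0.21 belongs to the repeated-measures model.

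The cost is revised analysis and power wording and one degree of freedom for each baseline slope in a model (one in each ANCOVA, two in the mixed model). No further children, visits or measurements are needed.

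### Parents know the allocation, yet parent BRIEF, SSIS and SRS are tested as efficacy and generalisation outcomes without being separated from teacher forms, so a positive parent scale cannot by itself show a training benefit

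*Combined protocol and SAP*

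**What the plan says.** All references are to the combined protocol and SAP.

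- **Design** (intervention paragraph under Recruitment & Diagnostic Procedures): "Children with ASD will be randomly assigned to either computer training or a waitlist control condition". For the trained group, "Ten training visits will occur over a 2-3-month period". Both groups are retested 2-3 months after baseline, "after which the waitlist group will be offered training if it is efficacious". No sham or active computer control is described.
- **Masking:** training visits are run by separate staff "so the assessment team may remain naïve to treatment status". In the Analyses section, EEG files with recoded IDs are checked for artifacts "by a staff member naïve to group assignment". Nothing is said about whether parents or teachers are masked.
- **Raters:** the note to the measures table says "Italicized measures are parent report", and this covers BRIEF, SSIS and SRS. The table rows and the Aim 3 paragraph show that teacher versions are also collected.
- **Analysis** (Statistical Analyses): the sentence on Hungry Donkey, Stroop and Change Task also covers "parent/teacher BRIEF scores pre/post training". The sentence on generalisation covers the theory-of-mind composite, SSIS and SRS, without naming the rater for the last two. One power figure is given "for behavioral and parent report tasks after training". No primary outcome, hierarchy or rule for reading parent and teacher forms is stated.

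**The concern.** A parent who has brought a child to ten training visits, or who is waiting for training to be offered, knows which group the child is in when completing a rating scale. On such a scale the rater's judgement is the measurement, so hope or disappointment can move the score with no change in the child. The plan takes care to limit this kind of bias for the assessment team and the EEG reader but says nothing about the informants.

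The exposed outcomes matter to the conclusions. BRIEF is the only measure of executive control at home and school, and SSIS and SRS are two of the three generalisation domains. With no rule on which rater's form counts, a parent scale that is significant alone could be read as efficacy or generalisation when training benefit and rater expectation are mixed in it.

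**Working it through.** **1. Can parents be naïve?** The design has a waitlist, ten visits for one group only, and training for the other group only after follow-up testing. Parental knowledge is inferred from these facts, not stated, but no other reading is workable.

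**2. Does the analysis remove the problem?** ANCOVA adjusts for baseline score. A shift that begins after allocation is absent at baseline, so it stays in the adjusted group difference. The one control outcome, Backward Digit Span, is a child performance task and cannot reveal a shift in a parent's ratings.

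**3. The plan's own figure.** Inputs from Statistical Analyses and Participants: 30 per group (N = 60), one covariate, alpha 0.05, power 0.8, detectable effect 0.37. Two-sided testing is assumed.
- Degrees of freedom: 1 and 60 − 2 − 1 = 57. Noncentrality = N × f².
- With f = 0.37: 60 × 0.1369 = 8.21, power 0.804.
- With f² = 0.37: 60 × 0.37 = 22.2, power 0.996.

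The figure reproduces as Cohen's f, although it is printed as f². That label is a separate matter. What matters here is that the sample size and model are confirmed.

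**4. Effect of a pure rating shift.** The documents give no size for it, so the shift b is an assumption. It is expressed in residual SD, that is, the SD of the post-test score after baseline adjustment. There is no true effect.
- Noncentrality = b × √(30/2) = b × √15 = 3.873b, on 57 df. Critical t = 2.002.
- An observed difference of 2.002/3.873 = 0.52 residual SD is enough for p < 0.05.

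| Assumed shift b | Noncentrality | Two-sided rejection rate |
|---|---|---|
| 0 | 0 | 5.0% |
| 0.2 | 0.775 | 11.9% |
| 0.3 | 1.162 | 20.8% |
| 0.4 | 1.549 | 33.1% |

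Nearly all rejections under a shift favour training: 11.5 of the 11.9 percentage points at b = 0.2.

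**5. Sensitivity to the unit.** If the shift is in raw SD, the noncentrality is 3.873b/√(1 − r²), where r is the baseline–post-test correlation (also assumed). For r from 0.3 to 0.7, the chance of a significant result favouring training, nominally 2.5%, is 12-19% at b = 0.2, 22-36% at 0.3 and 36-57% at 0.4.

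**6. Sensitivity to combining raters.** The plan does not say whether parent and teacher scores are tested separately. Suppose they were averaged, with no shift in the teacher score, equal SDs and an assumed cross-rater correlation of 0.3. A parent shift of 0.3 becomes 0.15/√((1 + 0.3)/2) = 0.15/0.806 = 0.19 SD of the average, and the rejection rate is about 11%, not 21%. The bias is diluted, not removed.

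**The case against.** The strongest reply is that informant ratings cannot be masked in a waitlist trial, that no formula in Statistical Analyses is wrong because of it, and that the underlying gap is the missing outcome hierarchy. ERP components come first in the analysis section and social measures second, and nothing says that a parent scale may carry a claim. That is fair as far as it goes. But the section gives no rule against it either, and a sentence on how to read each rater's form costs almost nothing.

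Four stronger readings are tempting and are not supported:

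- **That the plan has nothing to tell expectation from benefit.** It collects teacher versions of all three scales, a theory-of-mind composite from child tasks, and ERP data with masked artifact review. What is missing is a statement of how these bear on the parent results.
- **That parent ratings are set against fully blinded measures.** The plan says only that the assessment team may remain naïve, and the children know their own condition. The laboratory tasks are assessor-masked at best.
- **That the teacher forms are masked.** Nothing says so. They cannot be treated as a clean substitute.
- **That expectation alone would make the trial positive, with a chance of 25% to 57% that at least one of three parent scales is significant.** No decision rule defines a positive trial. Simulation at an assumed scale correlation of 0.5 does give roughly 0.25, 0.40 and 0.57 for shifts of 0.2, 0.3 and 0.4, but about 12% arises with no shift at all (about 6% in the favourable direction). That part is ordinary multiplicity, a different issue. The figures also presume that each parent form is tested alone.

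**Conclusion.** The concern holds as an interpretive gap that should be closed before the outcome data are analysed. Parents will know the allocation, their ratings are tested as efficacy and generalisation outcomes alongside assessor-administered tasks, and neither baseline adjustment nor the digit-span control deals with a shift in rating after allocation. A positive parent scale cannot by itself show a training benefit.

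The size is illustrative. The 12% to 33% range rests on an assumed shift of 0.2 to 0.4 residual SD, no true effect, 30 per group, a two-sided 0.05 test and a parent form tested separately. It shows that a modest shift would be enough to matter at this sample size, not that such a shift will occur. ERP and task outcomes are not affected by parental rating bias.

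**What to change.** In Statistical Analyses:

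1. Fit separate baseline-adjusted ANCOVAs for the parent and the teacher forms of BRIEF, SSIS and SRS.
2. Label the parent forms as unblinded and supportive.
3. State that conclusions on efficacy or generalisation need support from tasks given by naïve assessors (the executive tasks and the theory-of-mind composite) or from ERP data processed under masking.
4. Treat the teacher forms as corroboration without assuming that teachers are naïve. Ask families not to disclose the allocation, record on the form whether the teacher knew it, and report the teacher results with that information.

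**Cost:** analysis wording, a request to families and one item on an existing form; no new visit or assessor. The request to families cannot be enforced, which is why the item is needed. Teacher forms may be less complete and less sensitive to change, and conclusions on executive function at home will be supportive only.
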